8.3.3.4 Completed Subjects

A completed subject is considered to be a subject that completed all procedures as defined by the clinical investigation plan.

8.3.3.5 Subjects lost to follow-up

If a subject fails to appear for a follow-up examination, reasonable effort should be made to locate or contact them to at least to determine their health status while fully respecting the subject's right, followed by mandatory contacts with the patient's treating doctor for exchange information on the patient's health status. Reasonable effort consists of at least three attempts to contact the subject by

phone or post. These efforts should be documented in both the subject's source documents and CRF. So that the monitor can verify if the study center's attempted contacts with the patient and patient's family doctor were adequate.

8.3.3.6 Pregnancy

If a subject becomes pregnant between screening and surgery, she will be withdrawn from the study. If a subject becomes pregnant between surgery and the end of the study, she may remain in the study if she wishes. Her follow-up will be limited at the discretion of the Investigator until the end of the pregnancy as necessary to protect her health and that of the fetus/embryo. The pregnancy will be documented as an AE and as a protocol deviation. The pregnancy will be followed until the end to determine its outcome.

8.3.4 Point of enrollment

A subject is considered as being enrolled into the clinical investigation when he/she gives written consent to participate in this investigation.

8.3.5 Total expected duration of the clinical investigation

The estimated total duration of the study from first patient screened to last patient last visit is 25 months. At the start of the study, all patients enrolled in Switzerland will be requested to sign up for an additional follow-up of 2 years. These patients will automatically transition to the ARGOS-SC_Follow-up.

8.3.6 Expected duration of each subject's participation

The maximum duration of each subject's participation in this clinical intervention is 13 months. The point of enrollment is considered to be the time point at which potentially eligible subjects sign the informed consent form. Surgery will be performed within 28 days of enrollment. The subject will be followed-up for 12 months post-surgery to obtain data on safety and performance. At the start of the study, all patients enrolled in Switzerland will be requested to sign up for an additional follow-up of 2 years. These patients will automatically transition to the ARGOS-SC_Follow-up.

8.3.7 Number of subjects required

This exploratory investigation will enroll 24 patients.

The overall recruitment time is expected to last a maximum of 12 months.

Page 58 of 97

8.3.8 Informed Consent

Eligible patients may only be included in the study after providing written informed consent as described in Section 12.1. Failure to obtain signed informed consent renders the patient ineligible for the study.

8.3.9 Allocation of Patient Number

Each subject is uniquely identified in the study by a combination of his/her country identifier (e.g. DE for Germany and CH for Switzerland), site number and patient number. The number is assigned by the sponsor to the investigational site. Upon signing the Informed Consent Form, the subject is assigned a patient number by the investigator. The patient number will be composed of the abbreviation of suprachoroidal and 01 (SC01) (and a 3-digit string consisting of a 1-digit center identifier and a 2-digit patient identifier. This 2-digit patient identifier corresponds to the chronological order of enrollment in the center (e.g. the 3rd subject included in the study at site 1 in Germany will be patient DE-SC01-1-03). Once the patient number has been assigned to a subject, a number will not be reused even if the subject is a screen failure.

8.3.10 Methods and timing for assessing, recording, and analyzing parameters

During the study, subjects will attend 10 clinic visits, including 1 screening visit (up to 28 days prior to surgery), 1 surgery visit (day 0), and 8 follow-up visits (days 1, 3, 10, 30, 90, 180, 270 and 360). The assessment schedule in Table 1 summarizes all visits and the assessments to be performed at each. The visit window given in the table should be adhered to as closely as possible.

At the start of the study, all patients enrolled in Switzerland will be requested to sign up for an additional follow-up of 2 years. These patients will automatically transition to the ARGOS-SC_Follow-up (V10 – V13).

8.3.11 Safety

At each follow-up visit, the Investigator will examine the subject and record information about any new or ongoing adverse events, adverse device events or clinically significant anomalies. In addition, the Investigator or designated site staff will ask the subject non-leading questions to ascertain if the subject experienced any adverse events or adverse device events between visits.

Page 59 of 97

8.3.12 Performance

IOP level will be assessed at every follow-up visit in a series of 2 GAT standard measurements followed by 3 consecutive measurements with the ARGOS-SC system. From V05 (day 30) on, if available, additional 2 DCT measurements followed by 3 consecutive measurements with the ARGOS-SC system. **Optional:** At visits V06, V07 and V09, 24-hours measurements with GAT and ARGOS-SC will be done inpatient.

Patients will be given a MESOGRAPH reading device at Visit 01 in order to measure the IOP daily at home. Measurements shall be taken at least 4 times per day (morning, noon, afternoon, evening). The MESOGRAPH reading device will be connected to an external GSM module, which will transfer the measured value directly to a secure database. Investigators can log into the database in order to track the pressure levels of their patients as required. At every follow-up visit, site staff will examine the subject's hand-held reader device and download all readings recorded since the last visit. In addition, they will ask subjects non-leading questions to determine if any device deficiencies occurred since the last visit. All device deficiencies will be recorded on the device deficiency page of the CRF.

To ensure accuracy and comparability of the recorded parameters, all responsible site personnel will be thoroughly instructed on the agreed measurement methods.

To access the user acceptance of the implantation procedure and the general usability of the ARGOS-SC system, surgeons and personnel performing the ARGOS-SC system measurements will be asked to complete user acceptance questionnaires. The aim of these questionnaires is to gain more information about the level of user-acceptance of the ARGOS-SC system during implantation and during IOP measurement. The data collected with these questionnaires is only of exploratory nature and will not be included in the analysis. Results will provide the sponsor with data that could influence future device system improvements.

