6.3 Possible complications and adverse events

Complications may occur due to additional surgical manipulation of the eye while implanting the ARGOS-SC device. While it is possible to implant the device in a standalone procedure, for a first-inhuman trial, implantation will be combined with non-penetrating glaucoma surgery (NPGS). The complications which might occur during the implantation may also be associated with the standard non-penetrating glaucoma surgery. However, implantation of the additional device may increase their likelihood and/or severity. Nevertheless, it is assumed that these adverse events could be minimized or eliminated by surgeon training as well as following all of the instructions regarding implant handling and surgical procedure. Possible adverse events might be:

- Perforation/Rupture of the trabeculo-descement's membrane (TDM)
- Anterior chamber inflammation
- Hypotony
- Shallow anterior chamber
- Suprachoroidal hemorrhage
- Choroidal detachment
- Retinal detachment
- Hyphema
- Blebitis
- Iris incarceration in TDM
- Temporary visual impairment as a secondary effect caused by the adverse events described above.

It is assumed that in most cases, the complications that may arise following NPGS with combined ARGOS-SC implantation are expected to be temporary and manageable by medication.

For the clinical evaluation process, IOP management therapy and assessment of therapy success will be based solely on IOP values measured with Goldmann Tonometry and, when available, Dynamic Contour Tonometry. IOP values derived from the ARGOS-SC implant will in no case be used for therapy decisions as long as not validated.

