8.1.2 Description of the measures to be taken to minimize or avoid bias

No randomization or blinding/masking procedures will be used in this study. To avoid bias resulting from patient selection, all consecutive patients who potentially meet the eligibility requirements will be informed of the study and asked to participate. Those agreeing will undergo the informed consent procedure and if they consent, will be screened. All eligible patients will be enrolled.

There will be no control group for safety events. Incidence, nature and severity will be compared to literature of standalone NPGS. To allow assessment of performance, measurements of IOP with the ARGOS-SC sensor will be compared to those obtained with the standard GAT method and Pascal DCT at the same time point. To prevent possible influence of prior knowledge of the IOP value obtained with the ARGOS-SC, which is objectively displayed, measurements will always be made first with GAT/DCT. Data on all device deficiencies will be recorded.

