8.3.13.14 Intraocular pressure (IOP) measurement

Intraocular pressure will be measured using three techniques. Goldmann Applanation Tonometry (GAT) will be performed in the clinic at every visit and if available, Pascal Dynamic Contour Tonometry (DCT) at V05 through V09. ARGOS-SC measurements will be performed in the clinic at every visit and by the patient at home between the visits. Only GAT will be used to guide any treatment decisions. The GAT and DCT must be performed by as few dedicated investigators as possible at each site to reduce potential bias.

IOP measurement in the clinic

IOP measurement will be conducted at V02 through V09 as a series of 2x GAT (in case of a difference of more than 2mmHg, a third GAT-measurement is required) followed by 3x ARGOS-SC system. When series of measurements are made, GAT must always be used first to avoid potential operator bias. For the ARGOS-SC measurements the patient has to stay in the same position as for the GAT-measurements (chin on chin rest, forehead installed). From V05 through V09 additionally (if available), a series of 2x DCT (in case of a difference of more than 2mmHg, a third DCT-measurement is required)

followed by 3x ARGOS-SC will be performed after the series of GAT and ARGOS-SC measurements. For the ARGOS-SC measurements, the patient has to stay in the same position as for the DCT-measurements (chin on chin rest, forehead installed).

Optional: At V06, V07 and V09, the patient will be hospitalized for 24-hours measurements with GAT and ARGOS-SC. IOP measurements with ARGOS-SC will be done automatically via an external antenna. IOP measurements with GAT will be done every three hours, if it is possible even at night. If night measurements are not possible every three hours at night, the last measurement should take place between 22 and 24 o'clock and the three-hours rhythm should be resumed between 5 and 7 o'clock on the next morning.

ARGOS-SC system measurement by the subject at home

Subjects will receive detailed instruction in the use of the MESOGRAPH reading device. At V02, they will receive an individual MESOGRAPH reading device, a copy of the instructions for use and the Multiline Connector to perform self-tonometry at home. Subjects will be requested to perform at least 4 IOP measurements daily with the MESOGRAPH, one each in the morning after getting up, at noon, in the afternoon and in the evening before going to bed.

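### The GAT-first rule hides the same-session ARGOS-SC value from the tonometry operator but does not cover home ARGOS-SC readings

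*Protocol*

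**What the plan says.** **The threat and the control.** Protocol 8.1.2 states "No randomization or blinding/masking procedures will be used in this study". It then names the risk, "To prevent possible influence of prior knowledge of the IOP value obtained with the ARGOS-SC", and answers it with sequence: "measurements will always be made first with GAT/DCT". Protocol 8.3.13.14 repeats the rule for clinic series: "When series of measurements are made, GAT must always be used first to avoid potential operator bias". The same section adds that GAT and DCT are done by a small number of dedicated investigators per site. It also requires two readings by each method, with a third if they differ by more than 2 mmHg.

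**Access to home readings.** Patients are asked for at least four sensor readings a day at home. These go automatically to a database, and 8.3.12 says "Investigators can log into the database in order to track the pressure levels of their patients as required". The same permission appears in 8.3.13.14, in a footnote to Table 1 and in the footnotes to the SAP flow chart (2.10). At each follow-up visit site staff examine the reader and "download all readings recorded since the last visit" (8.3.12). In 8.3.13.14 they check its function and delete its stored data. Neither section says whether this happens before or after GAT.

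**What rests on the comparison.** SAP 2.9.1 makes agreement between GAT and ARGOS-SC at V02–V09 the primary endpoint. Protocol 9.5 counts the study a success if 70% of measurements agree within ±5 mmHg and no more than one of the 24 patients has a SADE.

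**The concern.** GAT is a manual reading, and the protocol itself accepts that an operator who knows the sensor value may be influenced by it. The control chosen acts only within a visit. An operator who has looked at a patient's home profile, or has seen the reader downloaded minutes earlier, arrives at GAT knowing roughly what the sensor reads in that eye.

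A pull of GAT towards that level narrows the paired differences. It therefore favours the device on the ±5 mmHg criterion. It could not be identified afterwards, because neither document provides for recording whether the operator had seen home readings before tonometry.

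**Working it through.** The plan gives no figure on this point to reproduce. The check is a comparison of sections, a count of the visits exposed, and an illustration of sensitivity.

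**1. Sections side by side.**

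| Question | Source | Answer |
|---|---|---|
| Is the paired, same-session sensor value hidden at GAT? | 8.1.2, 8.3.13.14 | Yes, by order |
| Are home readings hidden from the GAT operator? | 8.3.12, 8.3.13.14, Table 1 footnote, SAP 2.10 | No such statement; investigators have access |
| Who does GAT and DCT? | 8.3.13.14 | Dedicated investigators |
| Is download or clearing of the reader placed after GAT? | 8.3.12, 8.3.13.14 | Not stated |
| Are home readings kept out of the agreement analysis? | 9.11.2, SAP 3.7 | Yes for the per-protocol evaluation, but this does not keep them from the operator |
| Is DCT taken before any sensor reading? | 8.1.2 against 8.3.13.14 and Table 1 footnote 12 | 8.1.2 says yes; the procedure puts DCT after the first ARGOS-SC series from V05 |

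**2. Maximum exposure.** Inputs: 24 patients (8.3.7) and eight follow-up visits V02–V09 (8.1.1).

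- Planned patient-visits with a GAT–sensor pair: 8 × 24 = 192.
- Reader issued at V02 (8.3.13.14, 8.3.18): home readings can precede GAT at V03–V09, so 7 × 24 = 168.
- Reader issued at V01 (8.3.12; Table 1 also marks self-measurement from V01): V02 could be exposed too, so up to 192.

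These are ceilings. They assume no missed visit, and that someone looked before every GAT.

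**3. Illustration of sensitivity.** The pull *w* is assumed; the documents give no value. Let D = ARGOS-SC − GAT be normal with mean 0 and standard deviation SD. Let the home reading equal the clinic sensor value plus independent error e with standard deviation s. If the operator records GAT + w × (home − GAT), the recorded difference is (1 − w)D − w·e, so

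SD′ = √[(1 − w)²·SD² + w²·s²], and the share within ±5 is 2Φ(5/SD′) − 1.

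- True agreement 65%: SD = 5.35. With w = 0.10 and s = 0, SD′ = 0.90 × 5.35 = 4.82, giving 70.1%.
- True agreement 60%: SD = 5.94. With w = 0.20 and s = 0, SD′ = 0.80 × 5.94 = 4.75, giving 70.7%.
- With s of 2 to 4 mmHg these become 69.9–70.1% and 70.0–70.6%.
- With seven of eight visits exposed and s = 0: (7 × 70.1 + 65)/8 = 69.5%, and (7 × 70.7 + 60)/8 = 69.4%. Over s from 0 to 4 mmHg the ranges are 69.3–69.5% and 68.8–69.4%.

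Under these assumptions a modest pull moves the observed share by roughly 4 to 11 points. With seven of eight visits exposed, neither example reaches 70%.

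**The case against.** Several points on the other side stand.

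- **The order rule still works for what it directly addresses.** The sensor value paired with a given GAT reading is taken after it. A reader might infer that home access defeats the safeguard altogether. The documents do not support that: what can leak is the recent home level, not the paired value.
- **GAT-first is not the only bias control.** Few dedicated operators, duplicate readings with a tie-break, and instruction of site personnel in agreed methods (8.3.12) all reduce operator error. None of them keeps home readings from the operator.
- **Access is permitted, not required.** The download is assigned to site staff, who need not be the operator. It would be wrong to read 168 of 192 as a count of biased pairs, or to conclude that the result will be inflated.
- **Home readings are described as not comparable with clinic ones** (9.11.2), because times and conditions vary. That weakens them as an anchor but does not remove it: in the illustration, errors of 2 to 4 mmHg change the result little.
- **The study is exploratory and openly unmasked.** That argues against demanding full operator masking, though not against closing a gap in a control the protocol already adopts.
- **Safety.** Protocol 6.3 says "IOP values derived from the ARGOS-SC implant will in no case be used for therapy decisions as long as not validated", and 8.3.13.14 reserves treatment decisions to GAT. Sections 4.6 and 6.6 are softer: they rest decisions mainly on conventional tonometry and accept that home readings may prompt extra visits. Any change should therefore leave between-visit access in place.

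**Conclusion.** The point holds as a gap in coverage. The stated safeguard hides the same-session sensor value and is silent on home readings, which the same role may open at any time and which are handled at each visit in no fixed order relative to GAT. Any resulting bias would most plausibly favour the device on one of the two success criteria in 9.5.

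Whether bias occurs, and how large it would be, cannot be read from the documents. The step 3 figures depend on an assumed pull and zero mean difference; they show only that a borderline result could be sensitive. Exposure is at most 168 of 192 planned patient-visits if the reader is issued at V02, and up to 192 if at V01. The hand-out sections must be reconciled before that count can be settled.

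A related conflict needs no assumption about behaviour: from V05, DCT follows an ARGOS-SC series, contrary to the wording of 8.1.2. This is an inexpensive improvement worth making, not a flaw that invalidates the primary comparison.

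**What to change.** **Visit order (Protocol 8.1.2, 8.3.12, 8.3.13.14).** State that at each visit the person doing tonometry enters the GAT values before the reader is examined, downloaded or cleared and before the database is opened. State also that this person does not consult that patient's home readings before the visit's tonometry unless needed for patient safety. Database access between visits for follow-up stays. A same-day rule alone would not be enough, since readings seen the evening before inform the operator just as well.

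**Record and analyse exposure (CRF; SAP 4.6.1).** Add a CRF item on whether the operator had seen home readings since the last visit. Repeat the agreement analysis without the flagged pairs as a sensitivity analysis. This relies on self-report, and it shows how far the result depends on exposed pairs without correcting any bias.

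**DCT.** Reconcile 8.1.2 with the sequence in 8.3.13.14 and Table 1 footnote 12, for example by keeping the first-series sensor display from the operator until DCT has been entered.

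**Reader hand-out.** Reconcile V01 (8.3.12, Table 1) with V02 (8.3.13.14, 8.3.18).

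**Cost.** A few protocol sentences, site training, one CRF item and one sensitivity analysis. On visit days the home data are reviewed after tonometry instead of before.

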8.3.13 Assessments

8.3.13.1 Patient demographics/other baseline characteristics

Patient demographic and baseline characteristic data to be collected on all subjects include: year of birth, age, sex, race, pre-treatments and source of subject referral. This information will be collected at the Screening visit.

Page 60 of 97

8.3.13.2 Medical history

Relevant medical history/current medical condition data includes data regarding ongoing or significant previous ophthalmic and general medical conditions and procedures until start of ARGOS-SC pressure sensor implantation. Relevant medical history should be supplemented by review of the subject's medical chart and/or by documented dialog with the subject's referring physician. If possible, diagnoses and not symptoms are to be recorded.

8.3.13.3 Concomitant medication, treatments and devices

There are no restrictions for the use of concomitant medications required for ophthalmologic or systemic diseases during this clinical investigation. All medications including non-prescription medications used by the subject during the trial and medications in use at enrollment, will be documented in the subject's file and in the CRF, as will all diagnostic procedures and medical interventions. There are following recommendations:

30 days prior to surgery (advisable, but not mandatory)

Modification of the glaucoma therapy:

• If possible, stop prostaglandin drops

On day of surgery

Treatment in the ward:

- 1x antibiotic eye drops (e.g. Polyspectran[©])
- Topical Povidone-Iodine Solution
- Pilocarpine (1-2%) eye drops as required

Treatment in the Operation room

- 1x Local anesthetic eye drops (e.g. Oxybuprocaine)
- Acetylcholine or Carbachol solution as needed

Immediately postoperative:

- Steroid-antibiotic combination ointment or drop (e.g. lsopto-Max[©] or Tobradex[©])
- Protective eyepatch

Postoperative follow-up:

Treatment after discharge:

ARGOS-SC01 CIP Rev. G _20190625

- Avoid prostaglandin treatment until postoperative inflammation is resolved
- Non-steroidal anti-inflammatory or corticosteroid (surgeon's discretion) and antibiotic eye drops (e.g. Tobradex[©])
- Artificial tears as required

Month 1

- Protective eye-shield at night for one week (also daily, if necessary. In case of monocular vision: use transparent eye-shield)
- Non-steroidal anti-inflammatory or corticosteroid (surgeon's discretion) and antibiotic eye drops (e.g. Tobradex[©]) 6x daily, degressive reduction over 1 month or frequency at surgeon's discretion
- Artificial tears as required
- Minimum 4 weeks non-steroidal anti-inflammatory or corticosteroid eye drops or ointment and minimum 2 weeks antibiotic eye drops or ointment

Month 2

- Non-steroidal anti-inflammatory drops (e.g. Acular[©] or Nevanac[©]), 4x daily or frequency at surgeon's discretion

8.3.13.4 AEs/ADEs/SAEs/SADEs

All AEs/ADEs/SAEs/SADEs will be recorded starting with the implantation of the ARGOS-SC pressure sensor.

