8.3.16 Visit SC – Screening (Day -28 to 0)

Only patients who have already agreed to undergo non-penetrating glaucoma surgery will be approached by the trial team about participation in the study.

At the screening visit (SC), the Investigator will conduct the informed consent process (Section 12.1), ensuring that the subject has signed and received a copy of the patient informed consent (PIC) form before any study specific procedures are conducted. Once the PIC is signed, the subject will be assigned a patient number (Section 8.3.9) and the Investigator will determine if the subject meets the eligibility criteria, surgery (V01) will be scheduled and the sponsor will be informed.

In addition, the following procedures will be performed at the screening visit:

- Collection of background information about the subject including: demographics, medical history with prior treatments and current medications and indication for non-penetrating glaucoma surgery.
- Pregnancy test, when applicable
- Vision-related Quality of Life (VqoL) questionnaire
- Visual acuity (ETDRS)
- External eye photography
- Anterior Segment assessments (slit-lamp biomicroscopy, AS-OCT, gonioscopy)
- Posterior Segment assessments (biomicroscopy, PS-OCT and fundus photography)
- IOP measurement with GAT and if available DCT
- Instruct subjects on the need to report as soon as possible any SAEs occurring at any time throughout the study (starting from Visit 02 surgery)
- Complete the CRF.

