8.3.17 Surgery, Visit 01 (Day 0)

The following procedures may be carried out up to one day before surgery (in subjects already hospitalized for the surgery) or prior to surgery on the day of surgery:

• Verify that the subject continues to meet eligibility criteria

- For female subjects of childbearing potential: collect urine for pregnancy test. A test done within 24 hours prior to surgery must be negative
- Perform external eye photography

The following procedures are to be performed on the day of the surgery:

- Updating medical history (up to start of ARGOS-SC implantation)
- Recording of concomitant medications, device deficiencies or malfunctions (including those detected during device preparation) and any Aes (starting from the point of inclusion/signing of the informed consent)
- Non-penetrating glaucoma surgery and ARGOS-SC pressure sensor implantation (described in Section 8.3.12)
- Completion of the implantation procedure questionnaire (surgeon) and the CRF
- Complete the patient inclusion form and fax it to the sponsor
- Instruct subjects on the need to immediately report any SAE that may occur at any time during the study.
- Schedule Visit 2 (V02).

The duration of the subject's hospitalization following surgery is at the discretion of the Investigator. Durations of up to 6 days will not be considered to be SAEs.

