11.3 Recording of Adverse Events (AEs)

All AEs will be documented throughout the clinical trial as per ISO 14155, chap. 6.4.1, meaning from the point of inclusion/signing of the informed consent, until resolution or stabilization, or for a maximum of 7 days after the last subject has been discharged from the study.

All AEs will be reported on an Adverse Event Form, one for each Adverse Event, which is part of the CRF.

AEs will be collected with a non-leading question at each visit: "Have you had any new or worsening health problems since the last visit?" as well as by reporting those events directly observed and spontaneously reported by the subject. Clearly related signs, symptoms and abnormal diagnostic procedures should preferably be grouped together and recorded as a single diagnosis or syndrome whenever possible. Seriousness, severity (mild, moderate or severe), outcome and relationship to investigational device as well as expectedness and action taken will be recorded in the AE page of the CRF. Start and end date and time of the event will also be recorded. SAEs will be followed until resolution or stabilization. AEs will be followed until resolution or stabilization, or for a maximum of 7 days after the last subject has been discharged from the study.

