11.4 Reporting of Serious Adverse Events (SAEs)

The site must report the following events to the sponsor immediately after becoming aware of them:

- 1. Any SAE affecting a subject, regardless of its relationship to the device or the study-procedures (beginning with the implantation of the ARGOS-SC sensor)
- 2. A SADE affecting a user or third party (all)
- 3. A device deficiency that might have led to an SAE involving a subject, user or third party if suitable action or intervention had not been taken or if circumstances had been less fortunate (all)

If the site is uncertain as to whether an event is an SAE, they should report it to the sponsor as if it were.

The sponsor will report SAEs to the Competent Authority in accordance with ISO 14155, Annex X of Directive 93/42/EEC, its amendment Directive 2007/47/EC, Annex 7 of Directive 90/385/EEC, MEDDEV 2.7/3, the German Ordinance on Medical Device Vigilance (MPSV) and applicable local laws and

Page 85 of 97

regulations. Reporting modalities defined in the MPSV and MEDDEV 2.7.3 will be followed. All SAEs will be documented completely. SAEs for which a relationship to the study device or diagnostic or therapeutic procedures performed as part of the clinical trial or other conditions of the trial cannot be excluded will be reported to BfArM immediately using the SAE report form found on the BfArM website. A summary report for all other SAEs will be submitted to BfArM every three months or as requested by BfArM using the SAE summary table from MEDDEV 2.7.3.

Information reported on the SAE shall include:

- The date the event was reported to the sponsor
- The country
- Site and Patient ID
- The date the subject underwent implantation with the study device
- The date of event onset
- The affected organ system
- A description of the event
- Actions, treatments and patient outcome as a result of the event
- The date the event was first noticed by or reported to the investigator
- An assessment of the relatedness of the event to the procedure
- An assessment of the relatedness of the event to the device
- The expectedness of a SADE
- The event status
- The date of event resolution

Initial SAE reporting may be done by telephone or email, followed by the completed SAE form. Contact information is given on each SAE form and is available in the Investigator Site File.

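### Adverse-event recording starts at signed consent in Protocol 11.3 and 8.3.17 but at sensor implantation in 8.3.13.4, so events in between, including those in the earlier part of the operation, have no single classification

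*Protocol*

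**What the plan says.** Two sections start recording at consent. Protocol 11.3 covers all AEs "from the point of inclusion/signing of the informed consent, until resolution or stabilization", with a fixed outer limit. Protocol 8.3.17, on the day of surgery, asks staff to record "any Aes (starting from the point of inclusion/signing of the informed consent").

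One section starts recording at the sensor. Protocol 8.3.13.4: "All AEs/ADEs/SAEs/SADEs will be recorded starting with the implantation of the ARGOS-SC pressure sensor".

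Three neighbouring rules bear on the same interval:

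- Medical history (Protocol 8.3.13.2, updated under 8.3.17) is collected up to the start of implantation.
- Immediate SAE reporting from site to sponsor (Protocol 11.4) applies "beginning with the implantation of the ARGOS-SC sensor".
- At screening (Protocol 8.3.16) patients are told to report SAEs "starting from Visit 02 surgery", although surgery is V01 on day 0 and V02 is day 1.

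The AE row of Table 1 has its first entry at V01 and none at screening. The SAP flow chart (2.10) is the same. The SAP repeats the safety endpoints (2.9.2) and lists how AEs are tabulated (4.6.2), but does not say when an event begins to count.

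**The concern.** Sections 8.3.13.4, 11.3 and 8.3.17 govern the same activity and cannot all be followed. Sites that rely on different sections would classify the same event differently.

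The interval is not empty. The sensor goes in only after the pressure-lowering part of the operation (Protocol 4.7 and 8.3.14.1). Several of the events that Protocol 7.3 singles out for attention, such as suprachoroidal hemorrhage, choroidal detachment and hyphema, can arise during that earlier part.

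AE incidence is a secondary endpoint (8.1.3.2). There is no safety control group, and the planned comparison is with published results of standalone non-penetrating surgery (8.1.2). If some sites leave out events from the glaucoma-surgery phase, the study's incidence is not on a defined footing for that comparison.

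**Working it through.** No figure in the plan depends on this point, so the check is a comparison of the rules for each place an event can fall.

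| When the event occurs | Consent start (11.3, 8.3.17) | Implantation start (8.3.13.4 with 8.3.13.2) | SAE reporting (11.4) |
|---|---|---|---|
| After consent, before surgery (up to 28 days) | AE | Medical history if relevant, otherwise unrecorded | Not required |
| During surgery, pressure-lowering part | AE | Medical history if relevant, otherwise unrecorded | Not required |
| During steps done for the implant, before the sensor enters the eye | AE | Depends on when implantation is taken to begin | Same ambiguity |
| From insertion on | AE | AE | Required |

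1. **Rows 1 and 2 are the firm gap.** The rules give different answers for the same event. Section 8.3.17 also overlaps with itself: it updates history up to the start of implantation and records AEs from consent, so one event can qualify as both.

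2. **Row 3 arises because the start of implantation is not defined for recording.** Separating sclera and choroid with viscoelastic, and enlarging the flap or adding an incision, are done for the sensor but before it is inserted (4.7, 8.3.14.1, 8.3.14.2). The safety set (9.11.1) defines attempted implantation by the sensor entering the eye. The ADE definition (11.2.1) covers effects of implantation more generally.

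3. **Who is affected in the analysis.** The safety set requires that the sensor was introduced into the eye (Protocol 9.11.1, SAP 3.7). A patient in whom it never was is outside the set under either start. Analysed counts therefore change only for patients who go on to insertion.

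4. **Day 0.** The synopsis, Table 1 and 8.3.17 all collect AEs at V01, and the SADE endpoint in 8.1.3.2 runs from day 0. Row 4 is the same under every recording rule.

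5. **Pass/fail rule.** Protocol 9.5 allows at most 1 of 24 patients with a SADE. Let p be the true SADE rate, l the share of SADE patients not captured, and q = p(1 − l). The chance of passing is (1 − q)^24 + 24q(1 − q)^23. Both p and l are assumptions; the documents give neither. Example: p = 0.10 and l = 0.25 give q = 0.075 and 0.154 + 0.300 = 0.454.

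| Assumed p | l = 0 | l = 25% | l = 50% |
|---|---|---|---|
| 5% | 0.66 | 0.77 | 0.88 |
| 10% | 0.29 | 0.45 | 0.66 |
| 15% | 0.11 | 0.23 | 0.45 |

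The rule would be sensitive if SADEs were lost, but nothing in the documents shows a loss of this size. A SADE must be related to use of the device, so events in rows 1 and 2 will rarely qualify. The realistic exposure is row 3, and there the endpoint wording already includes the implantation itself.

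**The case against.** Much of the case against a wide reading stands.

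- A reader might infer from 8.3.16 that day-0 events are lost. The documents do not support that. The phrase is an instruction to patients about SAEs, it names surgery, and it reads as a wrong visit label. Staff collect AEs at V01 in any case.
- A reader might take perforation of the trabeculo-Descemet membrane as the natural example. It is a weak one. Exclusion criterion 12 lists it, so a patient in whom the surgeon finds it can be removed before insertion and replaced (8.1.5, 8.3.3.3), and is then outside the safety set.
- A reader might size the gap from the predecessor-device trial in Protocol 4.9.1, where 7 of 23 patients (30.4%) had surgical complications. That was another implant, placed with cataract surgery, and the protocol says those complications are not associated with this device. In five of the seven, complications occurred during implantation, which every recording rule here captures.
- A reader might infer that the SADE criterion could be tipped. No route is shown beyond the narrow one in row 3.
- Section 11.4 governs reporting and 8.3.13.4 governs recording. Different starts for the two are not in themselves a contradiction.
- Under the implantation start, relevant earlier conditions are still kept as medical history, so misclassification is likelier than outright loss. Differences between sites are a foreseeable result, not an observed one.

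None of this removes the conflict between 8.3.13.4 and 11.3 with 8.3.17. The reporting start in 11.4 also has a consequence of its own: read literally, an SAE during the glaucoma surgery before any sensor is implanted must be documented under 11.3 but need not be reported immediately to the sponsor under 11.4.

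**Conclusion.** The protocol contradicts itself on when AE recording starts, and the SAP does not resolve it. The disputed window is up to 28 days plus the part of the operation before the sensor step. The number of events in it cannot be derived from the documents and may be small.

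The effect is mainly on descriptive AE and SAE incidence, and on the comparison with standalone-surgery literature, among patients who go on to insertion. The SADE pass/fail count is less exposed, and day-0 collection is secure. This conclusion rests on reading 8.3.13.4 as a recording rule, as its wording says, and on treating the visit number in 8.3.16 as a slip.

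**What to change.** 1. Use signed consent as the single start for AE and SAE recording in 8.3.13.4 and Table 1, as 11.3 and 8.3.17 already do.
2. End the medical-history window at consent in 8.3.13.2 and 8.3.17, so that no event is both history and AE.
3. Align the SAE reporting start in 11.4 with the recording start.
4. Correct the visit label in 8.3.16; surgery is V01.
5. Add one CRF timing field with four levels: before surgery; during surgery before any implant-specific step; during implant-specific steps (viscoelastic separation, flap enlargement or extra incision, insertion); after insertion. Incidence can then be shown with and without the pre-implant phase, whichever matches the literature used.
6. Keep the SADE endpoint window as in 8.1.3.2, and state that it includes the implant-specific steps before insertion. Counting only from insertion would cut out surgical harms done for the device.

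Section 8.3.3.2 limits the data kept on patients who fail eligibility before surgery to dates and a reason. It should say how AEs after consent are handled for them.

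The cost is protocol wording, one CRF field and a slightly higher AE count.
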